***STUDY INFORMATION**

Title	CAB LA PrEP Cohort: Prospective Cohort Study to Assess Adherence and Effectiveness of, and Monitor for Hepatotoxicity and Resistance to, Cabotegravir for Pre-Exposure Prophylaxis in Europe		
Protocol version identifier	v1.2		
Date of last version of protocol	26-Jul-2024		
EU PAS (ENCEPP) register number	Study not yet registered		
Active substance	J05AJ04, cabotegravir		
Medicinal product	cabotegravir		
Product reference	Apretude		
Procedure number	EMEA/H/C/005756		
Marketing authorisation holder(s)	ViiV Healthcare B.V.		
Research question and objectives	Following the initiation of CAB LA for PrEP, the study will aim to assess usage patterns, adherence, effectiveness, safety of CAB LA for PrEP, and resistance among individuals who acquire HIV while on CAB LA for PrEP.		
Countries of study	Potential countries for inclusion: Belgium, France, Ireland, Italy, Spain, United Kingdom		
Author	PPD		

MARKETING AUTHORISATION HOLDER(S) *

Marketing authorisation holder(s)	ViiV Healthcare B.V.		
MAH contact person	PPD		

UNIQUE IDENTIFIER	221935		
TITLE	CAB LA PrEP Cohort: Prospective Cohort Study to Assess Adherence and Effectiveness of, and Monitor for Hepatotoxicity and Resistance to, Cabotegravir for Pre-Exposure Prophylaxis in Europe		
STUDY ACCOUNTABLE PERSON	- Epidemiology		
CONTRIBUTING AUTHORS	PPD , NEAT-ID PPD , NEAT-ID PPD , NEAT-ID PPD , ViiV Healthcare PPD , ViiV Healthcare PPD , ViiV Healthcare		
ASSET ID	GSK1265744		
GSK ASSET	Cabotegravir (PrEP)		
EFFECTIVE DATE	26-Jul-2024		
INDICATION	HIV Pre-exposure Prophylaxis (PrEP)		
SAFETY OBJECTIVE	YES		
DATA COLLECTION TYPE	SECONDARY		
TSS/PASS ASSESSMENT PERFORMED	Yes		

©2024 ViiV Healthcare group of companies or its licensor. All rights reserved. Unauthorised copying or use of this information is prohibited.

TABLE OF CONTENTS

PAGE

*ST	*STUDY INFORMATION				
LIS	LIST OF ABBREVIATIONS				
1.	RESPONSIBLE PARTIES				
2.	SYNOPSIS1	1			
3.	AMENDMENTS AND UPDATES14	4			
4.	MILESTONES	4			
5.	RATIONALE AND BACKGROUND 1 5.1. Background 1 5.2. Rationale 1	5 5 7			
6.	RESEARCH QUESTION AND OBJECTIVE(S)	7			

2. SYNOPSIS

Title: CAB LA PrEP Cohort: Prospective Cohort Study to Assess Adherence and Effectiveness of, and Monitor for Hepatotoxicity and Resistance to, Cabotegravir for Pre-Exposure Prophylaxis in Europe

Rationale and background:

Cabotegravir (CAB, GSK1265744) is a human immunodeficiency virus type-1 (HIV-1) integrase strand transfer inhibitor (INSTI), with attributes favourable for both HIV treatment and prevention indications. CAB, as a component of a dual antiretroviral maintenance therapy regimen in combination with the long acting (LA) formulation of Rilpivirine (RPV) LA, has been approved in several countries and regions (including the US, EU, Canada, and Australia) for the treatment of HIV-1 infection in adults.

ViiV Healthcare has developed oral CAB tablets and CAB LA extended-release suspension for injection for pre-exposure prophylaxis (PrEP) to reduce the risk of sexually acquired HIV-1 infection in individuals weighing at least 35 kg. In the pivotal Phase IIb/III studies HPTN 083 and HPTN 084, the PrEP regimen containing CAB LA dosed every 2 months was demonstrated to be superior to daily oral tenofovir disoproxil fumarate/emtricitabine (TDF/FTC) for HIV prevention in men who have sex with men (MSM), transgender women (TGW) and cisgender women.

The totality of data from the CAB PrEP pivotal and supportive clinical studies, pharmacokinetic (PK) modelling/simulation and the overall data from the CAB Treatment program has supported the use of CAB PrEP as a novel, well-tolerated, effective, LA PrEP agent. CAB LA for PrEP has been approved in several countries and regions (including the US, Australia, Zimbabwe, South Africa, Brazil, Botswana, and Malawi), and received market authorisation in the European Union by the EMA on 15 September 2023 for use in at-risk adults and adolescents weighing at least 35 kilograms (77 pounds) for PrEP to reduce the risk of sexually acquired HIV.

CAB LA for PrEP (Apretude) is given first as two initiation injections administered one month apart, and then every two months thereafter. Individuals can either start their treatment with Apretude, known as direct to injection (DTI), or take oral cabotegravir (Vocabria) for four weeks to assess how well they tolerate the drug, otherwise known as optional oral lead-in (OLI).

The Marketing Authorization Holder (MAH) proposes a five-year post authorization study to be conducted in collaboration with NEAT-ID Network, a well-established network of clinical sites across Europe. This prospective observational cohort study will aim to better understand the population receiving CAB LA for PrEP in routine clinical practice, usage patterns, adherence, post marketing clinical effectiveness, discontinuations, and monitor for resistance among individuals who receive an HIV diagnosis while on CAB LA for PrEP.

Research question and Objectives:

Following the initiation of CAB LA for PrEP, the study will aim to assess usage patterns, adherence, effectiveness, safety of CAB LA for PrEP, and resistance among individuals who receive an HIV diagnosis while on CAB LA for PrEP.

The specific objectives are to:

- 1) Describe the population initiating CAB LA for PrEP, including proportion of individuals who use OLI and proportion of those with DTI
- 2) Monitor for adherence by assessing the frequency of delayed and missed injections without oral PrEP
- 3) Monitor for incidence of HIV diagnosis while on CAB for PrEP and describe the timing of incident HIV diagnoses relative to timing of CAB PrEP usage
- 4) Monitor for occurrence of drug induced liver injury (DILI) and hypersensitivity reaction (HSR) following CAB LA injections
- 5) Evaluate incidence of and risk for developing resistance among individuals with an HIV diagnosis while on CAB LA for PrEP

Study Design:

This will be a 5-year long prospective cohort study of adults and adolescents \geq 35 kg initiating CAB LA for PrEP in real-world clinical setting in the EU.

Population

HIV-negative adults and adolescents (at least 12 years of age) \geq 35 kgs initiating CAB LA for PrEP initiating OLI or CAB LA injections.

Variables

The exposure of interest in this study is use of CAB for PrEP per the approved SmPC for CAB oral and LA formulations.

Primary outcomes of interest include:

- Incident HIV diagnoses
- Proportion of individuals receiving CAB LA PrEP who receive an HIV diagnosis after 6, 12, 24, 36, and >36 months of follow-up time
- Time to incident HIV diagnoses
- ART regimen and VL testing among CAB PrEP users with prevalent and incident infections
- Adherence and Durability
- Frequency of resistance to INSTIs and specific mutations

• Frequency of DILI and HSRs following CAB OLI and CAB LA injections assessed at 6, 12, 24, 36, and >36 months

Data sources

Data will be collected from participating European clinical sites within the NEAT ID Network. Data will be collected by electronic transfer of deidentified electronic medical data from each site.

Study size

The study aims to include a target of at least 500 participants initiating CAB LA for PrEP across Europe.

Data analysis:

Descriptive analyses will summarize baseline characteristics of study participants and covariables will be reported as frequencies/median (IQR) at baseline and at follow-up. Time to HIV diagnosis will be assessed using Kaplan-Meier curve. Cox proportional hazards models will be constructed to compare time to HIV diagnosis adjusting for participant characteristics. Adherence will be estimated using the date of injections over 6 and 12-month periods. Frequency of resistance will be described among individuals who acquire HIV while on CAB LA for PrEP.

Milestones:

3. AMENDMENTS AND UPDATES

Amendment or update no	Date	Section of study protocol	Amendment or update	Reason
1.1	19-Apr-2024	Sections 6-7, 10	Update	Incorporating comments raised by EMA in their assessment report of the initially submitted protocol.
1.2	25-Jul-2024	Sections 2, 4	Update	Updating milestone estimated dates, aligning study title throughout protocol, and minor formatting.

4. MILESTONES

Milestone	Estimated date
Draft Protocol Submission to EMA	December 2023
Final Protocol Submission to EMA	April 2024
Registration in the EU PAS register	August 2024
Study Start (after Protocol Approval)	August 2024
CCI	

5. RATIONALE AND BACKGROUND

5.1. Background

Across populations and pre-exposure prophylaxis (PrEP) regimens, oral PrEP significantly reduced the risk of human immunodeficiency virus (HIV) acquisition compared with placebo. Trials in men who have sex with men (MSM) with oral PrEP use of more than 70% adherence demonstrated the highest PrEP effectiveness (risk ratio = 0.30, 95% confidence interval: 0.21-0.45, P < 0.001) compared with placebo. Trials with low PrEP adherence did not show a significantly protective effect.¹ An effective, well-tolerated, long-acting (LA) PrEP agent could offer substantial advantages over currently available PrEP regimens, including daily oral tenofovir-based fixed drug combinations (FDC) that require long-term adherence for corresponding efficacy for PrEP. Long-acting PrEP regimens may ensure better adherence and efficacy among PrEP users.

Cabotegravir (CAB, GSK1265744) is a human immunodeficiency virus type-1 (HIV-1) integrase strand transfer inhibitor (INSTI), with attributes favourable for both HIV treatment and prevention indications. CAB, as a component of a dual antiretroviral maintenance therapy regimen in combination with the LA formulation of Rilpivirine (RPV) LA, has been approved in several countries/regions (including the US, EU, Canada, and Australia) for the treatment of HIV-1 infection in adults.

ViiV Healthcare has developed oral CAB tablets and CAB LA extended-release suspension for injection for pre-exposure prophylaxis (PrEP) to reduce the risk of sexually acquired HIV-1 infection in individuals weighing at least 35 kg. The totality of data from the CAB PrEP pivotal and supportive clinical studies, PK modelling/simulation and the overall data from the CAB Treatment program supports the use of CAB PrEP as a novel, well-tolerated, effective, LA PrEP agent. CAB LA for PrEP (Apretude) received market authorisation in the European Union by the EMA on 15 September 2023 for use in at-risk adults and adolescents weighing at least 35 kilograms (77 pounds) for pre-exposure prophylaxis (PrEP) to reduce the risk of sexually acquired HIV.²

Apretude is given first as two initiation injections administered one month apart, and then every two months thereafter. Individuals can either start their treatment with Apretude, known as direct to injection (DTI), or take oral cabotegravir (Vocabria) for four weeks as an optional oral lead-in (OLI) to assess how well they tolerate the drug. Oral cabotegravir may also be used as oral PrEP in individuals who miss planned dosing with CAB LA injection.²

Efficacy assessment from pivotal studies (HPTN 083 and HPTN 084), designed to assess the safety and efficacy of CAB PrEP when compared to the active comparator daily oral TDF/FTC for HIV PrEP in the most key affected populations globally (i.e., MSM and TGW [enrolled in HPTN 083] and cisgender women [enrolled in HPTN 084]) demonstrated superiority.^{3,4}

In 083, CAB PrEP demonstrated superior efficacy among MSM and TGW when compared to daily oral TDF/FTC (HR 0.34; 95% CI 0.18 to 0.62, two-sided p=0.0005), with an approximate 66% reduction in the rate of incident infections. There were 39 HIV

incident infections in the TDF/FTC group (incidence rate 1.22/100 PY) and 13 incident infections occurred in the CAB group (incidence rate 0.40/100 PY).³

In 084, CAB PrEP demonstrated superior efficacy among cisgender women when compared to daily oral TDF/FTC (HR of 0.11 (95% CI 0.04 to 0.31), p<0.0001) demonstrating an 89% reduction in the rate of incident infections for CAB. There were 36 HIV incident infections in the TDF/FTC group (incidence rate 1.85/100 PY) and 4 HIV incident infections occurred in the CAB group (incidence rate 0.20/100 PY).⁴

CAB tablets are indicated for short term PrEP to reduce the risk of sexually acquired HIV-1 infection in at-risk individuals weighing at least 35 kg. The tablets may be used as:

- OLI for one month to assess tolerability of CAB prior to administration of the injection.
- Oral PrEP in individuals who miss planned dosing with CAB LA injection.

CAB LA injections are indicated for PrEP to reduce the risk of sexually acquired HIV-1 infection in at-risk individuals weighing at least 35 kg.

Detailed dosing information on initiation and maintenance doses or OLI and injectable CAB, handling delayed or missed injection can be found in the Summary of Product Characteristic (SmPC).² CAB PrEP was well-tolerated with a safety profile comparable to the active comparator daily oral TDF/FTC in the pivotal studies, excluding the incidence of injection site reactions (ISR), which occurred more frequently in CAB participants.

Elevated aminotransferases have been observed with CAB during the CAB Treatment program in people with HIV, and hepatotoxicity is a known adverse drug reaction (ADR) for CAB. Possible or probable cases of drug-induced liver injury (DILI) have been observed on the CAB PrEP program and DILI has been observed in participants on CAB therapy for HIV treatment. DILI reported with PrEP demonstrates similar characteristics including being mild to moderate in severity and reversible upon discontinuation of CAB. Clinical and laboratory monitoring should be considered, and CAB should be discontinued if hepatotoxicity is confirmed, and individuals managed as clinically indicated.

Hypersensitivity reactions (HSRs) have been reported in association with integrase inhibitors including cabotegravir. These reactions were characterised by rash, constitutional findings and sometimes organ dysfunction, including liver injury. Apretude and other suspected medicinal products should be discontinued immediately, should signs or symptoms of hypersensitivity develop (including, but not limited to, severe rash, or rash accompanied by fever, general malaise, fatigue, muscle or joint aches, blisters, oral lesions, conjunctivitis, facial oedema, hepatitis, eosinophilia or angioedema). Clinical status, including liver aminotransferases should be monitored and appropriate therapy initiated.²

This 5-year prospective, non-interventional study across Europe will aim to understand the population receiving CAB LA for PrEP in real world clinical practice, usage patterns, adherence, post marketing clinical effectiveness, discontinuations, and monitor for hepatotoxicity related to administration of CAB for PrEP and HSR, and resistance among individuals who acquire HIV while on CAB PrEP. The data generated from this study will enhance our understanding of CAB LA for PrEP.

5.2. Rationale

The potential benefits of CAB as a new, LA PrEP regimen with superior efficacy as compared to an active comparator taken daily outweigh the potentially low risks of acquiring HIV and subsequent resistance development. There is a risk for HIV acquisition if the individual does not adhere to the CAB PrEP dosing schedule, and protective levels of CAB decrease to a level where HIV acquisition can occur. There may also be risk for HIV acquisition if the individual does not use other HIV-1 prevention strategies, including knowledge of HIV-1 status, regular testing for other sexually transmitted infections, condom use, etc. A warning and precaution are included in product labelling with recommendation that individuals should be counselled periodically to strictly adhere to the recommended CAB dosing schedule and the use of other prevention strategies. There is also a risk for the development of resistance in individuals with unrecognized or acute HIV-1 infection at the time of starting CAB PrEP.

In addition, there is risk of HIV-1 infection during or following CAB PrEP discontinuation, i.e. during the CAB exposure that is detectable >52 weeks post injection (PK tail), and subsequent emergence of CAB resistant HIV-1 strains. A warning and precaution are included in product labelling with recommendation for monitoring to clinically reassess individuals for risk of HIV acquisition and to test to confirm HIV negative status. Although not treatment limiting, CAB LA usage has the risk of hepatotoxicity and potential for HSRs. This 5-year long prospective, non-interventional study will aim to further understand and quantify the risks in real world clinical settings. The additional data generated will continue to inform clinical practice of CAB LA for PrEP usage.

6. RESEARCH QUESTION AND OBJECTIVE(S)

The study will aim to assess usage patterns, adherence, effectiveness, safety, and resistance among individuals initiating CAB LA for PrEP.

The specific objectives are to assess:

- 1) CAB LA for PrEP usage pattern:
 - a. Describe the population initiating CAB LA for PrEP by:
 - i. Baseline demographics (age, sex, gender, ethnic origin, geographic region, BMI)
 - ii. Risk factors for HIV acquisition: STI diagnoses, substance use including injection drug use
 - iii. PrEP: History of previous PrEP use
 - iv. OLI or DTI: proportion of individuals who use OLI prior to initiating injections and proportion of individuals DTI

- b. Describe the individuals initiating CAB OLI or CAB LA PrEP with undiagnosed HIV acquisitions by baseline demographics and PrEP history
- c. Describe oral PrEP used to cover planned, delayed or missed CAB LA injections
- d. Assessing the frequency of testing for HIV and methods used for HIV-1 diagnosis, as well as assessing the timing of HIV testing relative to CAB LA for PrEP initiation injections and maintenance injections

Undiagnosed (prevalent) HIV acquisitions will be defined as positive laboratory HIV antigen/antibody test or positive viral load (RNA assay) following first prescription of CAB OLI and separately, following first CAB LA for PrEP injection. The date of the assay should be at the time of the first prescription or injection while the result may be reported within 4-6 weeks after first prescription or injection. Prevalent HIV will be shown for those who received CAB OLI and those who used DTI strategy.

- 2) Treatment adherence (Medication errors): Monitor for adherence by assessing the frequency of delayed and missed injections without oral PrEP bridging
 - a. Delayed and missed injections (non-adherence to the scheduled dosing)
 - i. Determine the number of individuals that miss one or more consecutive injections without daily oral PrEP bridging
 - ii. Assess the mean and median number of injections missed during the 6-month and 12-month period without oral PrEP bridging
 - iii. Determine the number of individuals who receive the injections seven or more days later than their scheduled injection visit and median duration of delay
 - iv. Describe characteristics of the individuals that are non-adherent
 - b. Discontinuation of CAB LA PrEP
 - i. Determine the proportion of individuals who discontinue CAB LA PrEP after 6, 12, 24, 36, and >36 months
 - ii. Describe reasons for discontinuation of CAB LA PrEP
 - iii. Describe characteristics of the individuals who discontinue CAB LA PrEP
- 3) Effectiveness: Monitor for incidence of HIV diagnoses while on CAB for PrEP and describe the timing of incident HIV diagnoses with respect to timing of CAB for PrEP usage
 - a. Describe the proportion and number of incident HIV-1 infections while on CAB for PrEP among individuals in the following groups:
 - i. Infected during OLI
 - ii. Infected while on CAB LA: Incident HIV diagnoses, defined as HIV diagnosed after start of CAB injections while adhering to CAB LA PrEP regimen
 - b. Describe the timing of diagnosis of HIV with respect to timing of CAB for PrEP usage among individuals in the following groups:

- i. Infected during OLI
- ii. Infected while on CAB LA: Incident HIV diagnoses while adhering to CAB LA PrEP regimen
- c. Describe the proportion of incident infections among those who start with OLI and those who go to DTI separately and the timing of diagnosis of incident HIV for the overall group, and separately for the OLI and DTI groups.

The proposed study is a non-interventional study and will collect data from routine clinical practice and plans to capture all prevalent HIV-1 infections, including those captured during baseline. However, there are no plans to collect and store serum samples for subsequent testing as this is not part of standard of care.

- 4) Safety: Monitor for occurrence of DILI and HSRs following CAB LA injections
 - a. Describe the frequency of DILI after starting CAB LA at 6, 12, 24, 36, and >36 months after initiation as defined in Section 7.3.2.
 - i. Incidence proportion and rate of DILI following administration of CAB LA PrEP
 - ii. Incidence proportion and rate of CAB LA discontinuation due to DILI
 - b. Describe the frequency of HSR after starting CAB LA at 6, 12, 24, 36, and >36 months after initiation
 - i. Incidence proportion and rate of HSR following administration of CAB LA PrEP
 - ii. Incidence proportion and rate of CAB LA discontinuation due to HSR
- 5) Resistance: Evaluate incidence of and risk for developing resistance to integrase inhibitors (INSTI) among individuals in the following groups:
 - a. Incident HIV diagnoses while adhering to CAB LA for PrEP and development of resistance during treatment for HIV
 - b. CAB LA PrEP discontinued:
 - i. without subsequent oral PrEP & potential risk for HIV acquisition and viral resistance during CAB LA PK tail
 - ii. switched to oral PrEP and acquire HIV during the remainder of the follow-up period and develop resistance during subsequent treatment with ARVs
 - c. Individuals with undiagnosed prevalent HIV at initiation of CAB PrEP and subsequent emergence of resistance while on CAB monotherapy

Resistance testing: Since this is a non-interventional study aiming to capture standard of care (SoC) in real world settings, the study will not mandate resistance testing following discontinuation of CAB LA for PrEP. Health care providers following the SmPC and applicable local guidelines will decide what laboratory and resistance tests are to be conducted while an individual is on CAB LA for PrEP. Data thus generated, including available HIV-1 subtypes, will be captured

and analysed by the study team. Resistance will also be assessed among the individuals who are non-adherent to the injection regimen and acquire HIV.

7. **RESEARCH METHODS**

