7.3.2. Outcome definitions

1) Incident HIV diagnoses – confirmation of HIV positive status:

- Frequency (number and proportion) of incident infections during CAB OLI and while adhering to CAB LA PrEP regimen will be assessed. Additionally, frequency of incident infections will be assessed among those initiating CAB OLI and those initiating DTI.
- HIV diagnosis through at least one of the following:
 - Positive HIV-1 antigen/antibody lab results as well as an HIV-RNA-based test; if a combined testing strategy including both tests is not available, testing should follow local guidelines while taking Apretude.
 - One detectable viral load

Incident HIV is any new HIV diagnosis that occurs after the initiation of CAB PrEP, having confirmed HIV negative status using HIV RNA test, at the time of PrEP initiation.

Prevalent HIV is defined as any undiagnosed HIV at the time of PrEP initiation and will be defined as positive HIV antigen/antibody test and/or positive viral load from sample collected at the time of initiation, following first prescription of CAB OLI and separately, following first CAB LA PrEP injection. Note the test result may be reported within 4-6 weeks after the sample was collected. Proportion and number of persons with prevalent and incident HIV will be reported for CAB OLI and CAB LA PrEP separately.

This study is designed to capture data documented in health records in real world clinical settings, provision of 4-6 weeks after starting PrEP for diagnosis included above accounts for time needed to obtain the diagnostic testing results, confirmation and uploading it to the health record. Assessment of 'prevalent infection' vs. 'incident infection' will take into consideration the date the diagnostic test sample was collected and sent to the lab for testing.

2) Proportion of individuals receiving CAB LA PrEP with HIV diagnosis

3) Time to incident HIV diagnosis

- a) Time to diagnosis will be defined as months from first CAB LA injection or OLI till the first confirmed positive HIV-1 antigen/antibody result, detectable viral load and HIV diagnosis.
- b) Time to HIV diagnosis will be shown separately for individuals infected during OLI and while adhering to CAB LA injection schedule.
- 4) ART regimen and VL testing among CAB PrEP users with prevalent and incident infections:

ART regimen and VL testing during the follow-up period for the following groups will be described:

- a) Individuals with incident infections

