Frequency of undiagnosed prevalent HIV at CAB PrEP initiation will be assessed as described for objective 1. The primary effectiveness measure for objective 3 is proportion of individuals with incident HIV diagnosis during OLI and separately during CAB LA PrEP and will be calculated at 6, 12, 24, 36 months and over the entire length of follow-up. The proportion of incident infections among those who start with OLI and those who go to DTI will also be reported separately along with the timing of diagnosis of incident HIV acquisition for the overall group, and separately for the OLI and DTI groups.

Adherence patterns and characteristics of individuals with incident HIV diagnosis will be compared with those without incident HIV diagnosis, using t-test for continuous variables (Wilcoxon rank sum test for not normally distributed variables) or chi-square test for categorical variables. Participant characteristics significantly impacting acquisition of HIV based on univariate analysis will be selected for multivariable analysis. Risk for HIV acquisition and characteristics affecting risk for HIV acquisition will be assessed using negative binomial model with log-link function with binary outcome (HIV diagnosis vs not) if feasible.

Time to HIV diagnosis will be defined as time from first CAB LA PrEP injection to the first HIV diagnosis using laboratory antigen/antibody test, confirmed by viral RNA test. Time to HIV diagnosis will be assessed using Kaplan-Meier curve. Differences in time to diagnosis will be assessed by sex, gender, ethnicity (where available), geographic region, and risk factors (e.g. STI, previous PrEP usage) related, adherence to current PrEP to HIV acquisition. Additionally, time to diagnosis will be shown for people who acquired the infection while prescribed oral CAB lead in (if applicable). Time to diagnosis in this group will be defined as time from first CAB oral prescription to the first positive HIV-1 antigen/antibody lab result, confirmed by viral RNA test.

If feasible, Cox proportional hazards models will be constructed to compare time to HIV diagnosis by subgroup adjusting for additional variables (e.g., sex, ethnicity, (where available) geographic region).

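### The effectiveness numerator is defined in conflicting ways: infection on CAB LA is limited to adherent users in some places and not in others

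*Protocol*

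**What the plan says.** **Restricted wording.** Section 6, Objective 3(a)(ii), describes infection on CAB LA as "Incident HIV diagnoses, defined as HIV diagnosed after start of CAB injections while adhering to CAB LA PrEP regimen"; Objective 3(b)(ii) uses the same condition for timing. Section 7.3.2 item 1 says "Frequency (number and proportion) of incident infections during CAB OLI and while adhering to CAB LA PrEP regimen will be assessed", and item 3(b) says "Time to HIV diagnosis will be shown separately for individuals infected during OLI and while adhering to CAB LA injection schedule". Objective 5(a) and Section 7.3.2 item 6(c) carry the condition into the resistance groups.

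**Unrestricted wording.** Section 7.3.2 item 1 also states: "Incident HIV is any new HIV diagnosis that occurs after the initiation of CAB PrEP", given a negative RNA test at initiation. Section 7.6.1 repeats this under Objective 1. The primary effectiveness measure in Section 7.6.1 (Objective 3) is the proportion with incident HIV in the OLI period and, separately, during CAB LA PrEP. Objective 3(c) and the Kaplan-Meier endpoint have no adherence condition either.

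**Related rules.** Section 7.3.2 item 5 sets non-adherence at an injection 7 or more days late, or one or more missed without oral bridging. It sets discontinuation at two cycles, about 127 days, with neither injection nor bridging. Section 7.6.1 plans that "Adherence patterns and characteristics of individuals with incident HIV diagnosis will be compared with those without incident HIV diagnosis".

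**The concern.** The study is meant to describe effectiveness in routine care, where some injections will be late or missed. Section 5.2 itself says "There is a risk for HIV acquisition if the individual does not adhere to the CAB PrEP dosing schedule". If the case definition admits only adherent users, infections that the protocol expects are left out of the count because of something that happened after initiation. The reported incidence then describes on-schedule use, while a reader would take it as incidence among users in practice. Few events are expected, so one or two reclassified cases can change the message. The text also lets an analyst choose among three numerators: adherent cases only, all cases before discontinuation, or all cases after initiation.

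**Working it through.** **1. Follow one person through the definitions.** Take someone RNA-negative at initiation whose maintenance injection is 7 or more days late, or missed without bridging, and who is diagnosed before the discontinuation rule is met.

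- Objective 3(a)(i) and (b)(i), infected during OLI: not counted.
- Objective 3(a)(ii) and (b)(ii), Section 7.3.2 items 1 and 3(b), adherent on CAB LA: not counted.
- Discontinued under Section 7.3.2 item 5(c): not yet.
- Any new diagnosis after initiation (Sections 7.3.2 and 7.6.1): counted.
- Objective 3(c), by OLI or DTI start: counted.
- Primary measure in Section 7.6.1: depends on what being on CAB LA PrEP means. The only definition given is the adherent-only one in Objective 3.

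The same person is a case in some outputs and has no group in others.

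**2. Reproduce the plan's own figure.** In Table 1, N = 500 and a 1.00% rate give x = 5. The exact Clopper-Pearson limits come out at 0.3255% and 2.3181%, as printed. All 18 rows of Table 1 and all 5 of Table 2 reproduce to within rounding (0.0001 in the table's units). They hold for any numerator, so they do not show which definition was intended.

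**3. Effect if all starters form the denominator.** Let s be the share of cases that follow a late or missed injection. Then reported proportion = (1 − s) × true proportion. The documents give no value for s; 20%, 40% and 60% are assumed.

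| All cases of 500 | s = 0 | s = 20% | s = 40% | s = 60% |
|---|---|---|---|---|
| 5 | 1.0% (0.33 to 2.32) | 0.8% (0.22 to 2.04) | 0.6% (0.12 to 1.74) | 0.4% (0.05 to 1.44) |
| 10 | 2.0% (0.96 to 3.65) | 1.6% (0.69 to 3.13) | 1.2% (0.44 to 2.59) | 0.8% (0.22 to 2.04) |

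**4. Effect if off-schedule person-time is removed too.** Let q be the share of time off schedule and RR the rate ratio of off-schedule to on-schedule time. Restricted rate / all-user rate = 1 / [(1 − q) + q × RR]. With q = 0.20 (assumed):

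- RR = 1: 1 / 1.0 = 1.00
- RR = 2: 1 / 1.2 = 0.83
- RR = 5: 1 / 1.8 = 0.56

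With this denominator the rate is too low only if risk is higher off schedule.

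**5. How much one case weighs.** Section 5.1 gives 0.40 and 0.20 per 100 person-years on CAB in the two pivotal trials. Assuming that all 500 contribute 3 full years, 500 × 3 = 1500 person-years. Expected cases are 1500 × 0.20/100 = 3 to 1500 × 0.40/100 = 6. One excluded case removes 1/3 = 33% or 1/6 = 17%. As proportions of 500, 3 cases becoming 2 takes 0.6% to 0.4%, and 6 becoming 5 takes 1.2% to 1.0%.

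**6. Effect on the planned adherence comparison.** If CAB LA cases must be adherent, comparing adherence in cases and non-cases returns the definition and tells nothing about adherence and risk. The same holds for time to diagnosis by adherence.

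**The case against.** The strongest reply is that the analysis section governs, and it is unrestricted. The primary measure, Objective 3(c), the formal definition of incident HIV and the Kaplan-Meier endpoint name no adherence condition. The planned adherence comparison makes sense only if non-adherent cases are counted, which suggests that this was the intent. The study is descriptive, with no hypothesis test, and injection dates are collected (Section 7.5), so every version can be tabulated later. Infection despite on-schedule dosing is also a result worth reporting.

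Most of this stands, and it rules out saying that the primary estimate will be biased. It does not remove the conflict. Section 7.6.1 does not define being on CAB LA PrEP, and Objective 3, which it serves, defines infection in that state by adherence. That two counts can both be produced does not settle which one is reported as effectiveness, and a choice made once a handful of cases are known is open to challenge. The adherent-only result can be kept as a stratum without being the case definition.

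A reader might also infer that non-adherent users who acquire HIV have no resistance group. The documents do not support that. Section 6 says "Resistance will also be assessed among the individuals who are non-adherent to the injection regimen and acquire HIV", and group (b) in Section 7.6.1 covers incident HIV while on CAB LA PrEP with no adherence condition. Only Objective 5(a) and item 6(c) are out of line.

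**Conclusion.** The point holds as an internal contradiction in the case definition behind the primary effectiveness measure, with a risk of bias toward lower reported incidence. If the restricted definition is applied over all starters, the reported proportion falls by exactly the share of cases that follow late or missed injections. If off-schedule time is removed as well, the rate is too low only where risk is higher off schedule.

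The size cannot be derived from the documents. The values of s, q and RR are assumptions, the protocol gives no denominator for the adherent-only group, and the 3 to 6 cases assume pivotal-trial rates and full 3-year exposure for everyone.

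A reader might go further and infer that infections are counted only in adherent users, so that effectiveness is certain to be overstated. The unrestricted text in Sections 7.3.2 and 7.6.1 does not support that. Nor does Section 5.2 make non-adherence the main route to infection: it names it as a risk, unranked, next to not using other prevention strategies and infection during or after discontinuation.

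**What to change.** - In Section 6 (Objective 3(a)(ii) and 3(b)(ii)) and Section 7.3.2 (items 1 and 3(b)), delete the adherence condition from the case definition.
- In Section 7.6.1, define the primary numerator as every incident diagnosis from first CAB dose to discontinuation, with a matching denominator. Keep the OLI and CAB LA periods separate, as that section already does.
- Report diagnoses after discontinuation separately.
- Show on-CAB LA cases by adherence status at diagnosis (on time, late, missed), classified with the item 5(b) thresholds. The on-time stratum preserves the adherent-only result.
- Bring Objective 5(a) and Section 7.3.2 item 6(c) into line with resistance group (b) in Section 7.6.1. No new resistance group is needed.

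The cost is protocol wording, with the same change carried into any analysis plan. No new data are needed, because injection dates are already collected. Reported incidence may be slightly higher. The change should be made before the first interim results at 12 months.
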